the normal population.²⁰⁶ This criterion is commonly used in assessment of decision-making capacity²¹¹⁻²¹³ and has been shown to be more stringent than expert assessment of capacity.²⁰⁶ Generally, 15 to 20 minutes is required for completion.²¹⁴

As allowed under Virginia state law, an alternative procedure will be used to consent persons lacking the capacity to give informed consent, as determined by the MacCAT-CR or judged by the investigators. Investigators will seek to obtain consent from a legally designated substitute decision-maker. In every case, an effort will be made to obtain assent from the patient. Patients who decline to participate will not be enrolled regardless of their respective substitute decision-maker's desire. Readers should note, the protocol for this project has been submitted for review and approval to the VCU Office of Research Subjects Protection and formal approval is pending. More detailed information regarding human subjects protection and safety monitoring procedures is detailed in the *Human Subjects Narrative* (Form 424) and the *Data and Safety Monitoring Plan*. Readers should also note that, once approved, the study will be registered with ClinicalTrials.gov.

On giving informed consent, participants will be given baseline assessment materials to complete. Estimated time for the completion of baseline measures is 30-40 minutes. Project staff will make accommodations for persons with visual, motor, and other impairments.

Using randomization tables provided by our Biostatistician, [name], participants will be randomly assigned to either of two groups: (1) RAI or (2) RAI+. After randomization, a second appointment will be scheduled. Participants will begin treatment during their second appointment.

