Statistical Methods: A linear mixed-effects model will be used to model the CD-RISC scores over time for the RAI and RAI+ groups. The model will include fixed-effects for time at RAI+Booster initiation, conclusion, and long-term follow-up (e.g. 5, 6, and 11 months), group (RAI or RAI+) and the interaction between group and time. The model will also adjust for fixed-effects for injury severity, time postinjury, and education. Within-subject correlations in the CD-RISC scores over time will be modeled using a spatial power covariance pattern structure. Specific contrast statements will be used to test for a difference in the CD-RISC change scores between the treatment groups at both RAI+Booster initiation and conclusion as well as RAI+Booster initiation and long-term follow-up at a significance level of .05.

Power Analysis: Data obtained by our group indicated that the mean CD-RISC increased from a baseline value of 21.1 units to a mean of 28.4 units post-treatment (Difference=7.3), followed by a decline to 25.5 at the 3-month follow-up (Difference=2.9), with a standard deviation (SD) of the change score equal to 5.0. Considering a conservative SD of 6.0, this study will require 138 participants (n=69 per group) using a two-sample t-test performed at the 0.05 significance level to achieve 80% power. This effect translates to an effect size d=2.9/6.0=0.48, which is typically considered a moderate effect size.

Hypothesis 2: Participants in the RAI+ group will show better adjustment and lower levels of emotional distress as compared to persons in the standard RAI group.

Statistical Methods: Separate mixed-effects models, similar to that outlined in the methods for Hypothesis 1, will be used to model the responses for the MPAI-4 Adjustment Index and the BSI-18 GSI scores over time for each group. Specific contrast statements will be used to test the hypotheses of interest, each assuming a significance level of .05. Using a similar 40% decrease between the baseline to post-treatment values observed in our pilot study, we would expect the RAI+ to ameliorate declines in the MPAI-4 Adjustment and BSI-18 GSI scores by 1.7 and 2.6 points, respectively. Considering a conservative SD of 7.0, the 138 participants enrolled would provide power of 29% and 58% for the two outcomes, if analyzed by a two-sample t-test at the 0.05 level.

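### The primary test uses raw CD-RISC change from booster start; adjusting for CD-RISC scores already collected before the booster would be a cheap gain in precision on a test that is valid as planned

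*Combined protocol and SAP*

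**What the plan says.** Under E. Data Analysis, Hypothesis 1, the mixed model takes CD-RISC at three visits as outcomes: "The model will include fixed-effects for time at RAI+Booster initiation, conclusion, and long-term follow-up (e.g. 5, 6, and 11 months". In Study Procedures, item 6 of the IRB application, these are the 3-, 4- and 9-month assessments after RAI. The primary inference is: "Specific contrast statements will be used to test for a difference in the CD-RISC change scores between the treatment groups", from booster start to booster end and from booster start to long-term follow-up. On covariates: "The model will also adjust for fixed-effects for injury severity, time postinjury, and education". Within-person correlation follows a spatial power pattern.

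The sample size takes a planned difference of 2.9 points from the pilot, "with a standard deviation (SD) of the change score equal to 5.0", and continues: "Considering a conservative SD of 6.0, this study will require 138 participants (n=69 per group".

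Item 6 schedules CD-RISC in both arms at intake, after RAI, and 3, 4 and 9 months later, and gives both arms the same seven sessions before the booster. Section D6 fixes the order: "On giving informed consent, participants will be given baseline assessment materials to complete"; randomisation comes next; then "After randomization, a second appointment will be scheduled. Participants will begin treatment during their second appointment". Intake is therefore the only score taken before randomisation.

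**The concern.** Three CD-RISC scores exist in both arms before their scheduled treatment diverges. Intake and post-RAI are not in the primary model. Booster start enters only by subtraction, which fixes its slope at 1. When the true slope is below 1, subtraction removes too much, and a regression adjustment has smaller variance.

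The three listed covariates do not fill this gap. They are time-constant main effects, so with complete data they cancel from a within-person change. A reader of the model description could think that the primary contrast is covariate-adjusted when in effect it is not.

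What is at stake is precision, mainly at 9 months, where the correlation with booster start is likely to be weakest and where the trial's sustainability question is answered.

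**Working it through.** **Inputs.** Difference 2.9, pilot change SD 5.0, planning SD 6.0 and 69 per arm (Hypothesis 1, Power Analysis). Pilot RAI-arm SDs: 8.1 at baseline, 6.9 post-treatment, 7.8 at 3 months (pilot outcome table in the literature review). No between-visit correlation is reported.

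**The plan's own figure.** A two-sided two-sample t-test at 0.05, difference 2.9, SD 6.0 and 69 per arm gives 80.5% power. The 138 stands.

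**Covariates.** On one simulated complete dataset, generalised least squares with the planned terms gave contrasts of -1.1906 and -1.2223, identical to the raw differences in mean change.

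**Formula.** With booster-start SD sx, later SD sy and correlation r, the change variance is SDc² = sx² + sy² - 2·r·sx·sy. The variance after adjustment is sy²(1 - r²). Their ratio is the fraction of contrast variance left. With equal SDs it simplifies to (1 + r)/2.

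**(A) Pilot SDs 6.9 and 7.8** (the pilot's post-treatment to 3-month interval standing in for booster start to follow-up).
- SDc 5.0: r = (47.61 + 60.84 - 25)/107.64 = 0.775; ratio = 60.84 × (1 - 0.601)/25 = 0.971, a cut of 3%. Power goes from 92.3% to 93.0%.
- SDc 6.0: r = (47.61 + 60.84 - 36)/107.64 = 0.673; ratio 0.924, a cut of 8%. Power goes from 80.5% to 83.4%.

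**(B) Equal SDs, change SD 6.0.** r = 1 - 36/(2·SD²) = 0.622, 0.704 and 0.726 at SD 6.9, 7.8 and 8.1. The ratios are 0.811, 0.852 and 0.863, cuts of 14-19%. Power goes from 80.5% to 86-88%.

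**(C) The plan's spatial power structure, calibrated to 0.775 or 0.673 over 3 months.**
- Booster start to 4 months (1 month): r = 0.775^(1/3) = 0.919 or 0.673^(1/3) = 0.876; cut (1 - r)/2 = 4% or 6%.
- Booster start to 9 months (6 months): r = 0.775² = 0.601 or 0.673² = 0.453; cut 20% or 27%.
- Intake adds nothing: under spatial power, once the booster-start score is known, an earlier score carries no further information.
- If 27 of 96 per arm are lost, all after booster start (14 before 4 months, 13 more before 9 months; the timing is assumed), the cuts become 4-5% and 15-22%.

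**(D) Constant correlation r, equal SDs, booster-start plus intake.** The ratio is (1 + 2r)/(2(1 + r)): 0.688 at r = 0.6 and 0.718 at r = 0.775, cuts of 31% and 28%.

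**In standard-error terms.** A ratio of 0.971 is a reduction of 1 - √0.971 = 1.5%; 0.727 is 1 - √0.727 = 15%; 0.688 is 1 - √0.688 = 17%.

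**Exposure to a real pre-booster gap.** For each point of lasting arm difference at booster start, the adjusted contrast credits (1 - slope) points to the booster, where slope = r·sy/sx. In (A) the slopes are 0.876 and 0.761, giving 0.12-0.24. In (C) the credit is 0.08-0.12 at 4 months and 0.40-0.55 at 9 months. The change contrast credits none.

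**The case against.** The strongest case against has four parts.

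First, nothing is broken. The test is valid, the sample size reproduces, and change from booster start answers the maintenance question directly. That stands, and it limits this to a suggestion.

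Second, the only scenario built entirely on reported SDs, (A), gains just 3-8%, while adding intake pays only under a constant correlation that the plan's spatial power structure does not assume. That stands as well. A reader might infer that gains of about 36% are on offer. The documents do not support this: with correlations in the pilot-implied range, a cut that large needs all three earlier scores and a correlation constant over time.

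Third, booster start is measured after randomisation and the available text describes no blinding. If knowing one's arm opened a lasting gap before the booster, the adjusted test would credit part of it to the booster, most of all at 9 months under (C), where the precision gain from the booster-start score is also large. This is a real trade-off. It is the reason to keep the planned contrast beside the adjusted one. Intake carries no such risk.

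Fourth, a simple covariance analysis would drop people without a booster-start score whom the mixed model can keep. This is met by fitting the adjustment in a joint likelihood model.

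Protection against chance imbalance at booster start is not a separate benefit; it is the same precision loss seen conditionally.

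**Conclusion.** The point holds as an efficiency improvement worth considering. Adjusting for booster-start CD-RISC reduces contrast variance (not standard error) by about 3-8% with the pilot SDs and by 14-19% with equal SDs and change SD 6.0. Under the plan's covariance structure it is 4-6% at 4 months and 20-27% at 9 months. Intake brings the cut to 28-31% only if correlation does not decay with time. These figures illustrate assumptions and are not bounds; they rest on pilot SDs and on a pilot correlation of 0.67-0.78 inferred from the change SD.

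Two stronger readings should be resisted. A reader might infer that the planned test is biased or has the wrong type I error; it does not. A reader might also take the decaying correlation in (C), with its change SD of √(2 × 60.84 × (1 - r)) = 7.0-8.2 at 9 months, as proof that 138 is too few. The plan sizes on a change SD of 6.0, and the documents give no 6-month change SD against which to test that.

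**What to change.** 1. Prespecify the primary estimate as the RAI+ minus RAI difference in CD-RISC at 4 and 9 months, adjusted for the booster-start score with a separate coefficient at each visit, and also for the pre-randomisation intake score.
2. Fit it in a likelihood model that retains participants with a missing earlier score, for example with the earlier scores as additional outcomes whose means are common to both arms.
3. Keep the planned change-from-booster-start contrast as a sensitivity analysis and report arm means at booster start. A lasting pre-booster gap would show there and in a divergence between the two analyses.
4. Before finalising, take the post-treatment to 3-month CD-RISC correlation from the pilot data to see which scenario is realistic.

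Covariate-by-time terms, a different covariance structure and the same form for the secondary outcomes ("Separate mixed-effects models, similar to that outlined in the methods for Hypothesis 1, will be used") are optional; no gain has been shown for them.

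The cost is SAP wording and model code, since every score is already scheduled. The statistical price is the exposure described above: about 0.1-0.55 points credited to the booster per point of lasting pre-booster gap.

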The proposed investigation differs from prior VCU research in several important ways. First, in response to recommendations made by research participants, Scientific Advisors, and Advisory Board members, the intervention period has been extended with three booster sessions. Boosters will be patient-focused and personalized to address the original RAI topics that were most relevant to the individual, as described in the *Intervention* section which follows. Furthermore, the project will thoroughly evaluate the sustainability of treatment gains by extending the follow-up period from three to nine months. The research design will compare the benefits of the original intervention (RAI) to an expanded, more person-centered intervention (RAI+).

B. Objectives

- 1. to evaluate the short and long-term efficacy of two structured outpatient intervention programs (RAI vs. RAI+) on resilience
- 2. to evaluate the short and long-term impact of intervention on emotional well-being and postinjury adjustment with the RAI vs. the RAI+
- 3. to evaluate the short and long-term impact of the RAI and the RAI+ on abilities including problem solving, communication, and stress management
- 4. to determine if demographic, lifestyle, injury, or treatment response information can predict maintenance of gains

C. Hypotheses

- 1. **Primary:** Participants receiving the booster (RAI+ group) will report higher levels of resilience in comparison to individuals in the standard RAI group.
- 2. Participants in the RAI+ group will show better adjustment and lower levels of emotional distress as compared to persons in the standard RAI group.
- 3. Additionally, participants in the RAI+ group will report greater abilities in the areas of problem solving, communication, and stress management relative to persons in the standard RAI group.
- 4. A participant's demographic, lifestyle, injury, and treatment response information will be predictive of maintenance ability.

D. Methodology

D1. Stage of Research

VCU's previous work with the RAI was best labeled as an "Intervention Development" project.

The present proposal is best labeled as falling within the "Intervention Efficacy" stage of research,

as the primary goal is to evaluate whether the RAI+ is feasible, practical, and has the potential to

yield sustainable and positive outcomes over and above the benefits of the RAI. The present

proposal also seeks to identify individual characteristics associated with positive outcomes. The

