Additional quality control procedures will be implemented for booster sessions with each

therapist. As indicated in the Intervention section, booster sessions are person-centered and thereby

highly individualized. Audio-recordings will be made for the three booster sessions and reviewed

with [name] to ensure that key areas are covered as outlined in the manual. Every six months

thereafter, quality control procedures will be repeated.

Data collection procedures: Demographic, injury severity, and history information will be

collected at baseline using TBIMS standard procedures. For RAI and RAI+ participants, outcome

measures will be obtained prior to treatment (baseline) and following completion of the RAI.

Outcome measures for RAI+ participants will be obtained at the start and completion of the booster,

and six months following completion of the booster sessions. Measures for RAI participants will be

obtained at three, four, and nine months post-RAI treatment. Data collection will occur within the

same timeframe for both RAI and RAI+ participants as outlined in the figure that follows.

Project timeline: The major activities for the research project are sequentially delineated in the

Plan of Operation section.

E. Data Analysis

Descriptive statistics (e.g., means, standard deviations, proportions) will be calculated for all

measures at designated time intervals. Analyses will be performed using the university licensed

statistical program SAS v.9.3 (© 2002- 2010; SAS Institute Inc.; Cary, NC). The following table

provides a description of major statistical analysis procedures, emphasizing priority areas related to

research hypotheses. Information is provided regarding statistical hypotheses, statistical methods,

power analysis and sample size estimates. Analyses evaluating the RAI+ are based on the intent-to-

treat principle if drop-out is assumed as missing at random or missing completely at random.

Hypothesis 1 – Primary: Participants receiving the booster (RAI+ group) will report higher levels of resilience in comparison to individuals in the standard RAI group.

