Hypothesis 3: Participants in the RAI+ group will report greater abilities in the areas of problem solving, communication, and stress management relative to persons in the standard RAI group. **Statistical Methods:** Two additional mixed-effect models, similar to the first three, will be used to

model the MPAI-4 Ability scores and the 13-Item Stress Test scores over time for each group. Again, a specific contrast statement will be used to test the hypothesis of interest at a significance level of α = .05. In a similar fashion to Hypothesis 2, a 40% decrease between the observed baseline to post-treatment values yields differences of 1.6 and 0.9 for the MPAI-4 Ability Index and the 13-Item Stress Test. Considering a conservative SD of 7.0 and 2.0, respectively, the 138 participants enrolled would provide power of 27% and 75% for the two outcomes, if analyzed by a two-sample t-test at the 0.05 level.

Hypothesis 4 (exploratory): A participant's demographic, lifestyle, injury, and treatment response information will be predictive of maintenance ability.

Statistical Methods: Separate linear regression models will be used to determine the relationship between each of the demographic, lifestyle, injury, and initial RAI response characteristics and both the change in the 5 and 6 month CD-RISC scores, as well as the change in the 5 and 11 month CD-RISC scores. Assuming 69 participants in the RAI group complete the study and 8 predictor variables are in the linear regression model, this analysis will have 80% power to detect effect sizes of f^2 =0.12, which is considered a moderate effect size.

Power analyses relating to the primary hypothesis indicate minimum group sizes of 69 participants.

If we allow for a maximum of 10% attrition, then an additional 8 individuals per treatment group

(16 individuals total) should be recruited (138/(1-0.1)-138 = 15.3) for a total sample size of 154.

F. Feasibility F1. Project Staff

Personnel effort levels are based on thorough consideration of our prior experience conducting

similar projects. Following is information on responsibilities of personnel allocating >5% effort:

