Following our strategy with previous longitudinal studies of resilience (under review, *Archives of Physical Medicine and Rehabilitation*), individual growth curve analyses will be used to assess the relationships between caregivers' resilience and the longitudinal caregiver and patient characteristics. These models will include correlated random intercept and slope effects. Separate models will be fit with time, each caregiver and patient characteristic, and the interaction of these variables. Similar models will be fit without the interactions, and any interaction or individual

characteristic significant at the 0.05 level will be candidates to be entered into the final model. A backwards selection procedure will be performed so that all remaining characteristics have a p-value <0.05. The continuous time variable will remain in the model regardless of statistical significance. A random effect will be included to adjust for the different study sites and all inferences will be adjusted for the estimation of the random effects using a Kenward-Rogers adjustment.²⁵³

The SAS software will be used for all analyses except the LCLMM analysis, which will be performed using the 'lcmm' package in R.²⁵¹ All inferences will be made at the 0.05 level and all statistical models, with the exception of the ANOVA and Pearson chi-squared tests, are able to incorporate data that is missing at random. An adjustment for multiple comparisons will not be made due to the exploratory nature of the study.²⁵⁴

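### The primary hypothesis is tested by two unranked CD-RISC contrasts at .05 with no success rule, and the one-test sample size is not tied to either contrast

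*Combined protocol and SAP*

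**What the plan says.** The hypothesis labelled primary (grant text, C. Hypotheses and E. Data Analysis) is: "Participants receiving the booster (RAI+ group) will report higher levels of resilience in comparison to individuals in the standard RAI group". It names no time point. Objective 1 covers both horizons: "to evaluate the short and long-term efficacy of two structured outpatient intervention programs (RAI vs. RAI+) on resilience".

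The Statistical Methods for Hypothesis 1 specify a linear mixed model for CD-RISC at booster start, booster end and long-term follow-up, given as about 5, 6 and 11 months. The model has group, time and their interaction, and a spatial power covariance. Group differences in change are then tested "at both RAI+Booster initiation and conclusion as well as RAI+Booster initiation and long-term follow-up at a significance level of .05".

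The Power Analysis says that "this study will require 138 participants (n=69 per group) using a two-sample t-test performed at the 0.05 significance level to achieve 80% power". Its inputs come from the pilot RAI group, whose mean rose from 21.1 to 28.4 after treatment, "followed by a decline to 25.5 at the 3-month follow-up (Difference=2.9), with a standard deviation (SD) of the change score equal to 5.0". The SD is then raised to 6.0.

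The IRB application (Study Population, sample size justification) keeps 69 per group and changes only the attrition allowance, from 10% (154 enrolled) to 28% (192 enrolled). It adds no rule for combining the two contrasts.

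**The concern.** One primary claim is served by two tests, and the plan does not say what counts as success. Three rules fit the text: either contrast suffices, both are required, or the two are reported as separate claims. They have different error rates and different power, and the plan chooses none of them.

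The two contrasts also answer different questions. A gain seen only at the end of the boosters and a gain that lasts to 11 months support different conclusions, in a trial whose title names both efficacy and sustainability. Followed as written, the plan would let the primary claim rest on whichever contrast turned out significant.

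The sample size does not settle the matter. It describes one t-test without saying which contrast that is. The interval that supplied the 2.9 runs from the end of RAI to three months later, which is when the boosters begin, so it lies before both contrasts.

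**Working it through.** **1. The plan's own figure.** Inputs from the Power Analysis: difference 2.9, SD 6.0, alpha .05, power 80%. The normal approximation gives n = 2(1.96 + 0.842)² × 6.0² / 2.9² = 67.2, so 68 per group. The exact t calculation gives 68.2, so 69 per group, with 80.5% power at 69. The text does not state sidedness; a one-sided test would need only 54, so the calculation is two-sided. 138/0.90 = 153.3 (154 enrolled) and 138/0.72 = 191.7 (192 enrolled). All of the plan's figures reproduce.

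**2. Correlation between the contrasts.** Let p be the one-month correlation under spatial power, c1 = Y6 − Y5 and c2 = Y11 − Y5. Then, in units of the common variance:
- Var(c1) = 2(1 − p)
- Var(c2) = 2(1 − p⁶)
- Cov(c1, c2) = 1 − p − p⁶ + p⁵

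At p = 0.9 this gives 0.159 / √(0.200 × 0.937) = 0.367. Over all p, the correlation has a minimum of 0.34 (p about 0.72) and tends to 0.50 as p approaches 0.

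**3. Error and power under each rule** (bivariate normal, critical value 1.96 for each test):

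| Rule | Error | Power at 69 per group, 2.9/6.0 on both contrasts |
|---|---|---|
| Either suffices | Favouring RAI+: 4.5-4.7%, against 2.5% for one test. Either direction: 9.1-9.4% | about 92-94% for at least one |
| Both required | not inflated | about 68-70% jointly |
| Two separate claims | .05 for each claim | 80.5% each |

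If both were required, 80% joint power would need about 84-86 completers per group.

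**4. One SD for two intervals.** The ratio of the 5-to-11 month change SD to the 5-to-6 month change SD is √[(1 − p⁶)/(1 − p)]. It is 1.40 at p = 0.5, 2.16 at p = 0.9 and 2.30 at p = 0.95. A single SD of 6.0 therefore cannot in general describe both contrasts.

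**5. Illustration.** Assumptions: the cross-sectional SD is 6.9 or 7.8 (the pilot RAI group at post-treatment and at follow-up); the pilot change SD covers three months; the true difference is 2.9 on each contrast. With cross-sectional SD s and three-month change SD d, p³ = 1 − d²/(2s²). For d = 6.0 and s = 6.9, p³ = 1 − 36/95.22 = 0.622 and p = 0.854. The one-month change SD is then 6.9√[2(1 − 0.854)] = 3.73, and the six-month change SD is 6.0√(1 + 0.622) = 7.64.

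| Three-month SD | Cross-sectional SD | SD, 5 to 6 months | SD, 5 to 11 months | Power, 5 to 6 | Power, 5 to 11 |
|---|---|---|---|---|---|
| 6.0 | 6.9 | 3.73 | 7.64 | over 99% | 60% |
| 6.0 | 7.8 | 3.66 | 7.83 | over 99% | 58% |
| 5.0 | 6.9 | 3.03 | 6.59 | over 99% | 73% |
| 5.0 | 7.8 | 3.00 | 6.70 | over 99% | 71% |

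On these assumptions the sample is ample for the short contrast and short of 80% power for the long one, so the choice of which to test first matters.

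**The case against.** The best defence is that no error is inflated unless either contrast alone may carry the primary claim, and the plan never says that it may. Objective 1 asks about short-term and long-term efficacy, which fits two separately reported answers. The defence stands to this extent: the inflation is conditional, and a reader who inferred that the plan runs a 9% false-positive rate would go too far. The hypothesis is also directional, so the relevant excess is 4.5-4.7% against 2.5%. What remains is that the rule is unstated, and leaving it unstated permits the unfavourable reading.

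The contrast sentence might be read as requiring both results. Its wording lists which visits are compared; it does not define success. If both were required, the 80% power statement would not apply.

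Two other sentences might seem to settle the question. "Specific contrast statements will be used to test the hypotheses of interest, each assuming a significance level of .05" belongs to Hypothesis 2, and its word for each refers to secondary hypotheses, not to the two primary contrasts. "An adjustment for multiple comparisons will not be made due to the exploratory nature of the study" comes from the caregiver module, which is a different study.

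It is also fair to say that the 2.9 has a rationale. It is 2.9/7.3 = 40% of the pilot gain, and the Hypothesis 2 text uses a similar 40% for the declines that RAI+ is expected to offset. So 2.9 is apparently the decline that the boosters are assumed to prevent. The interval to which it applies is still missing.

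Finally, a reader might conclude that the trial is underpowered for its primary claim. The documents do not support that: 80.5% is correct if 6.0 is the SD of the contrast tested, and the lower figures rest on the assumptions in the illustration.

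**Conclusion.** The point holds as a missing decision rule and a missing link between the power calculation and a contrast. The arithmetic behind 69, 138, 154 and 192 is sound. The excess false-positive risk arises only under the either-suffices rule. Requiring both contrasts costs about 10-12 points of power relative to the stated 80%, if 2.9/6.0 holds for both. The error figures depend only on the planned covariance and hold for any monthly correlation. The power figures of about 58-73% for 5 to 11 months, and over 99% for 5 to 6 months, are illustrative: they need the pilot change SD to be a three-month SD and the 2.9 difference to apply to each contrast.

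Severity: should-fix. One sensible reading carries no inflation and the repair is short, but a rule chosen after the comparative results are known would not protect the primary claim.

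**What to change.** Before any comparative analysis, add to the analysis plan:

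- **Success rule.** Name one of the two CD-RISC contrasts as primary, tested at two-sided .05. Test the other at .05 only if the first is significant. The sponsor chooses the order.
- **Power.** State which contrast the 2.9-point difference and the SD of 6.0 describe, and restate power for the contrast tested first.
- **If two separate claims are intended,** say so, and do not call either one alone success on the primary hypothesis.

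The cost is a few sentences and one restated power calculation, with no extra participants. The downside is that the second contrast becomes descriptive if the first fails. If 5 to 11 months goes first, its restated power may be below 80%.

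Testing each contrast at .025 would also control error (4.7-4.8% over both directions), at a higher price. Power per contrast falls from 80.5% to 71.6% at 69 per group. Restoring 80% takes 83 completers per group, or 166/0.72 = 230.6, so 231 enrolled at 28% attrition against the planned 192.
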